5.3. Lifestyle Considerations

5.3.1. Contraception (If Applicable)

The investigator or his or her designee, in consultation with the participant, will confirm that the participant has selected an appropriate method of contraception for the individual participant and his or her partner(s) from the permitted list of contraception methods ([Section 10.4](#)) and will confirm that the participant has been instructed in its consistent and correct use. At time points indicated in the SoA, the investigator or designee will inform the participant of the need to use highly effective contraception consistently and correctly and document the conversation and the participant's affirmation in the participant's chart (participants need to affirm their consistent and correct use of at least 1 of the selected methods of contraception). In addition, the investigator or designee will instruct the participant to call immediately if the selected contraception method is discontinued or if pregnancy is known or suspected in the participant or partner.

5.4. Screen Failures

Screen failures are defined as participants whose parent(s)/legal guardian(s) have consented for them to participate in the clinical study but are not subsequently assigned to investigational product. A minimal set of screen failure information is required to ensure transparent reporting of screen failure participants to meet the Consolidated Standards of Reporting Trials (CONSORT) publishing requirements and to respond to queries from regulatory authorities. Minimal information includes demography, screen failure details, eligibility criteria, and any AE or SAE recorded from signing the informed consent until the time of determination of screen failure.

Individuals who do not meet the criteria for participation in this study (screen failure) may not be rescreened.

5.5. Temporary Delay Criteria

[figure not shown]
The following conditions are temporary or self-limiting and a participant may be vaccinated and/or have blood drawn in the study once the condition(s) has/have resolved and no other exclusion criteria are met.

The blood draw prior to vaccination should take place on the same day as the vaccination.

5.5.1. Criteria for Temporarily Delaying Vaccine Administration

- Current febrile illness (body temperature $\geq 38.0^{\circ}\text{C}$ [$\geq 100.4^{\circ}\text{F}$]) or other acute illness within 48 hours before investigational product administration.

PFIZER CONFIDENTIAL

- Receipt of short-term (<14 days) systemic corticosteroids. Investigational product administration should be delayed until systemic corticosteroid use has been discontinued for at least 28 days. Inhaled/nebulized, intra-articular, intrabursal, or topical (skin or eyes) corticosteroids are permitted.

5.5.2. Criteria for Temporarily Delaying Immunogenicity Blood Draw

- Receipt of antibiotic therapy within 72 hours before blood draw. Topical antibiotics are permitted.

[figure not shown]
6. STUDY INTERVENTION

Study intervention is defined as any investigational intervention(s), marketed product(s), placebo, or medical device(s) intended to be administered to a study participant according to the study protocol.

For the purposes of this protocol, the term investigational product may be used synonymously with study intervention.

6.1. Study Intervention(s) Administered

20vPnC is a sterile liquid suspension formulation containing saccharides from pneumococcal serotypes 1, 3, 4, 5, 6A, 6B, 7F, 8, 9V, 10A, 11A, 12F, 14, 15B, 18C, 19A, 19F, 22F, 23F, and 33F individually conjugated to CRM₁₉₇. CCI

Investigational product will be supplied by Pfizer as prefilled syringes. Each syringe will be packaged in a carton with a label and a tamper-evident seal, and will be labeled as required per country requirement (refer to the investigational product manual [IP manual]).

6.1.1. Administration

All participants will receive a single dose of 20vPnC at Visit 1.

The 0.5-mL dose of 20vPnC will be administered intramuscularly into the left leg (option for Cohort 1 only) or left arm by a designated site staff member. All other vaccinations (if given) should be administered into a limb other than the site of 20vPnC injection. The location of the injection of each vaccine administered (investigational product and other) will be recorded.

Standard vaccination practices must be observed and vaccine must not be injected into blood vessels. Appropriate medication and other supportive measures for management of an acute hypersensitivity reaction should be available in accordance with local guidelines for standard immunization practices.

Administration of investigational products should be performed by an appropriately qualified, Good Clinical Practice (GCP)-trained, and vaccine-experienced member of the study staff (eg, physician, nurse, physician's assistant, nurse practitioner, pharmacist, or medical assistant) as allowed by local, state, and institutional guidance.

Investigational product administration details will be recorded on the case report form (CRF).

6.1.2. Medical Devices

In this study, medical devices being deployed are the 20vPnC prefilled syringes.

Instructions for medical device use are provided in the IP manual.

Medical device deficiencies, including those resulting from malfunctions of the device, must be detected, documented, and reported by the investigator throughout the study. Please refer to [Section 8.3.9](#) for details.

6.2. Preparation/Handling/Storage/Accountability

1. The investigator or designee must confirm appropriate temperature conditions have been maintained during transit for all study interventions received and any discrepancies are reported and resolved before use of the study intervention, as applicable for temperature-monitored shipments.

PFIZER CONFIDENTIAL

CCI

A large rectangular area of the page is completely redacted with a solid red color, obscuring several paragraphs of text that would normally be present here.

6.2.1. Preparation and Dispensing

See the IP manual for instructions on how to prepare the investigational product for administration. Investigational product should be prepared and dispensed by an appropriately qualified and experienced member of the study staff (eg, physician, nurse, physician's assistant, nurse practitioner, pharmacy assistant/technician, or pharmacist) as allowed by local, state, and institutional guidance.

PFIZER CONFIDENTIAL

A horizontal bar consisting of three black rectangular blocks of varying widths, positioned below the 'PFIZER CONFIDENTIAL' text, obscuring the page number.

6.3. Measures to Minimize Bias: Randomization and Blinding

Since all participants will receive 20vPnC at Visit 1, this will be an open-label vaccination and will be prepared and administered by a site staff member or designee.

6.3.1. Allocation to Study Intervention

Laboratory personnel performing the immunologic assays will be blinded to the visit information until all assays have been completed and assay results finalized.

Each participant will receive a single dose of 20vPnC; however, the investigational product will be assigned using an interactive response technology (IRT) system (interactive Web-based response [IWR]). The site personnel (study coordinator or specified designee) will be required to enter or select information including but not limited to the user's identification (ID) and password, the protocol number, and the participant number. The site personnel will then be provided with a dispensable unit (DU) or container number when investigational product is being supplied via the IRT system. The IRT system will provide a confirmation report containing the participant number and DU or container number assigned. The confirmation report must be stored in the site's files.

The study-specific IRT reference manual and IP manual will provide the contact information and further details on the use of the IRT system.

6.4. Study Intervention Compliance

All doses of investigational product will be administered by the appropriately designated study staff at the investigator site.

6.5. Concomitant Therapy

[figure not shown]
[figure not shown]
6.5.1. Prohibited Concomitant Vaccines and Treatments

- Receipt of any investigational vaccines, drugs, or medical devices is prohibited during study participation.
- Receipt of nonstudy pneumococcal vaccine is prohibited during study participation.
- Receipt of blood/plasma products, immunoglobulins, and/or immunosuppressive therapy (including a ≥ 14 -day course of systemic corticosteroids) is prohibited through Visit 2.

6.5.2. Permitted Concomitant Vaccines and Treatments

- Influenza vaccine is permitted at any time during influenza season in this study. However, if feasible, it is recommended that influenza vaccine be administered at least 14 days before or after 20vPnC administration.
- Receipt of quadrivalent meningococcal conjugate vaccine is permitted only after the blood sample is collected at Visit 2.

PFIZER CONFIDENTIAL

- Receipt of other licensed nonstudy vaccines (except pneumococcal vaccine as described above) is permitted. However, if feasible, it is recommended that licensed nonstudy vaccines be administered at least 14 days (for nonlive vaccines) or at least 28 days (for live vaccines) before or after 20vPnC administration.
- Use of topical anesthetic is permitted.
- The use of prophylactic antipyretic/pain medication, while permitted, is not recommended on the day of investigational product administration (before or after vaccination).
- Inhaled/nebulized, topical (skin, eyes, or ears), or localized injections of corticosteroids (eg, intra-articular or intrabursal administration) are permitted during participant participation in the study.
- Prescription and nonprescription medications, vitamins, minerals, and herbal remedies are permitted during the study.

6.5.3. Recording Prior and Concomitant Vaccines and Treatments

The name, location, and date of administration for any nonstudy vaccinations received from the time of signing of the ICD to Visit 2 will be collected and recorded in the CRF.

For Cohorts 1 and 2, confirmation in the source documents of 3 or more prior doses of 13vPnC with the date of administration of the most recent (third or fourth) dose of 13vPnC is to be recorded on the CRF. For Cohorts 3 and 4, the date of administration of the most recent dose of 7vPnC or 13vPnC will be recorded on the CRF, if available.

Only medications taken to treat SAEs or NDCMCs from the time of signing of the ICD to the final visit (approximately 6 months after vaccination at Visit 1) will be collect and recorded in the CRF.

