- a. This telephone contact should occur approximately 6 months after study vaccination; this contact should be attempted for all participants who have received study vaccination, unless the parents/legal guardians have withdrawn consent.
- b. For Cohorts 1 and 2, information on the prior vaccination with 13vPnC will also be recorded. For Cohorts 3 and 4, information on prior vaccination with 7vPnC or 13vPnC will be recorded, if available. See [Section 6.5.3](#) for details.
- c. Record only concomitant medications used to treat SAEs and NDCMCs.
- d. The investigator or designee will inform the participant of the need to use highly effective contraception consistently and correctly until 28 days after the dose of investigational product and document the conversation and the participant's affirmation in the source notes.
- e. For Cohorts 1 and 2: ~5 mL; for Cohorts 3 and 4: ~10 mL.
- f. Blood sample will be collected prior to vaccination.
- g. Remind the participant's parent(s)/legal guardian(s) that the use of prophylactic antipyretic/pain medication, while permitted, is not recommended on the day of investigational product administration (before or after vaccination).
- h. Administer permitted routine pediatric vaccinations (as applicable) after the investigational product into a limb other than the site of the 20vPnC injection. Prohibited and permitted vaccines are described in Sections [6.5.1](#) and [6.5.2](#), respectively.
- i. The participant's parent(s)/legal guardian(s) will record prompted local reactions and systemic events and antipyretic/pain medication in an e-diary for the 7 days following vaccination. The participant's parent(s)/legal guardian(s) will be instructed to contact the study staff if the participant experiences severe redness or swelling >14 caliper units, severe pain at the injection site (left leg [option for Cohort 1 only] or left arm), a fever >40.0°C (>104.0°F), or an emergency room visit or hospitalization.
- j. Designated site staff will review e-diary data online at frequent intervals (daily is optimal) for the 7 days following vaccination to evaluate participant compliance and as part of the ongoing safety review.
- k. An NDCMC is defined as a disease or medical condition, not previously identified, that is expected to be persistent or otherwise long-lasting in its effects.

PFIZER CONFIDENTIAL

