11. Receipt of blood/plasma products or immunoglobulins (including hepatitis B immunoglobulin) or planned receipt through the last planned blood draw in the study (through Visit 2).

Prior/Concurrent Clinical Study Experience:

12. Participation in other studies involving investigational drug(s), investigational vaccines, or investigational devices within 28 days prior to study entry and/or during study participation. Participation in purely observational studies is acceptable.

Diagnostic Assessments:

Not applicable.

Other Exclusions:

[figure not shown]
13. Children or grandchildren who are direct descendants of investigator site staff members or Pfizer employees who are directly involved in the conduct of the study.

5.2.2. Cohort 3 and Cohort 4

Medical Conditions:

1. History of severe adverse reaction associated with a vaccine and/or severe allergic reaction (eg, anaphylaxis) to any component of the investigational product, or any diphtheria toxoid-containing vaccine.
2. Significant neurological disorder or history of seizure (excluding febrile seizure) or significant stable or evolving disorders such as cerebral palsy, encephalopathy, hydrocephalus, or other significant disorders.
3. Major known congenital malformation or serious chronic disorder.

PFIZER CONFIDENTIAL

4. History of microbiologically proven invasive disease caused by *S pneumoniae*.
5. Known or suspected immunodeficiency or other conditions associated with immunosuppression, including, but not limited to, immunoglobulin class/subclass deficiencies, DiGeorge syndrome, generalized malignancy, HIV infection, leukemia, lymphoma, or organ or bone marrow transplant.
6. Bleeding diathesis or condition associated with prolonged bleeding that would, in the opinion of the investigator, contraindicate intramuscular injection.
7. Congenital, functional, or surgical asplenia.
8. Other acute or chronic medical or psychiatric condition including recent (within the past year) or active suicidal ideation or behavior or laboratory abnormality that may increase the risk associated with study participation or investigational product administration or may interfere with the interpretation of study results and, in the judgment of the investigator, would make the participant inappropriate for entry into this study.
9. Pregnant or breastfeeding female participants.

Prior/Concomitant Therapy:

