8.2.1. Participant Electronic Diary

The participant's parent(s)/legal guardian(s) will be asked to monitor and record local reactions, specific systemic events, fever, and antipyretic/pain medication taken for 7 days, each evening following the study vaccination using an e-diary (in a provisioned device or application on a personal device). This allows recording of these assessments only within a fixed time window, thus providing an accurate representation of the participant's experience. Data on local reactions, specific systemic events, fever, and use of antipyretic/pain medication reported in the e-diary will be transferred electronically to the e-diary vendor, where they will be available for review by investigators, their qualified designees, and sponsor staff at all times via an internet-based portal. At intervals agreed to by the vendor and Pfizer, these data will be transferred electronically to Pfizer for analysis and reporting.

The daily e-diary data will not be captured in the CRF. However, if a participant is withdrawn because of prompted events reported in the e-diary, the event(s) should be recorded on the AE page of the CRF, regardless of whether the investigator considers the event(s) to be clinically significant.

The investigator or designee must obtain stop dates for any local reactions or specific systemic events ongoing on the last day that the e-diary was completed. The stop dates should be entered in the CRF.

Investigators (or an appropriately qualified designee) are required to review the e-diary data online at frequent intervals (daily is optimal) to evaluate participant compliance and reported events as part of the ongoing safety review.

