8.10.1. Visit 1 (Vaccination 1, Day 1)

Prior to vaccination:

- Obtain a personally signed and dated ICD indicating that the participant's parent(s)/legal guardian(s) has been informed of all pertinent aspects of the study before performing any study-specific procedures.
- Assign a participant number via the IRT.
- Obtain and record the participant's demographic information (including date of birth, sex, race, and ethnicity). The complete date of birth (ie, DD-MMM-YYYY) will be collected as permitted per local regulations to critically evaluate the immune response and safety profile by age.
- Perform a clinical assessment including medical history; record any findings on the medical history CRF.
- Measure and record the participant's temperature as appropriate for the age of the child, according to routine local practice (°F/°C).
- Confirm receipt of 3 or more prior doses of 13vPnC and record the date of prior administration of the most recent (third or fourth) dose of 13vPnC for Cohorts 1 and 2 only. Record the date of administration of the most recent dose of 7vPnC or 13vPnC for Cohorts 3 and 4, if available.

- Perform urine pregnancy test for female participants of childbearing potential (see [Section 8.2.4](#)).
- For participants of childbearing potential, instruct the participant to use appropriate contraceptives until 28 days after administration of investigational product and document the conversation and the participant's affirmation in the participant's source document.
- Ensure and document that all of the inclusion criteria and none of the exclusion criteria are met and that none of the temporary delay criteria are met.
- Assign an investigational product container number via the IRT. This must be the last step before proceeding. A site staff member will prepare the investigational product according to the IP manual.

After investigational product container number assignment:

- Collect a blood sample of approximately 5 mL for Cohorts 1 and 2, and approximately 10 mL for Cohorts 3 and 4, for immunogenicity assessments prior to vaccination.
- Administer a single 0.5-mL injection of 20vPnC into the left leg (option for Cohort 1 only) or left arm.

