<h3>Assessment of Intensity</h3> 
The investigator will make an assessment of intensity for each AE and SAE reported during the study and assign it to 1 of the following categories:
 
 Mild: An event that is easily tolerated by the participant, causing minimal discomfort and not interfering with everyday activities. Moderate: An event that causes sufficient discomfort and interferes with normal everyday activities. Severe: An event that prevents normal everyday activities. An AE that is assessed as severe should not be confused with an SAE. Severe is a category utilized for rating the intensity of an event; and both AEs and SAEs can be assessed as severe. 		

An event is defined as “serious” when it meets at least 1 of the predefined outcomes as described in the definition of an SAE, NOT when it is rated as severe.

GRADE	If required on the AE page of the CRF, the investigator will use the adjectives MILD, MODERATE, or SEVERE to describe the maximum intensity of the AE. For purposes of consistency, these intensity grades are defined as follows:	
1	MILD	Does not interfere with participant's usual function.
2	MODERATE	Interferes to some extent with participant's usual function.
3	SEVERE	Interferes significantly with participant's usual function.

Assessment of Causality

- The investigator is obligated to assess the relationship between study intervention and each occurrence of each AE/SAE.
- A “reasonable possibility” of a relationship conveys that there are facts, evidence, and/or arguments to suggest a causal relationship, rather than a relationship cannot be ruled out.
- The investigator will use clinical judgment to determine the relationship.
- Alternative causes, such as underlying disease(s), concomitant therapy, and other risk factors, as well as the temporal relationship of the event to study intervention administration will be considered and investigated.
- The investigator will also consult the IB and/or product information, for marketed products, in his/her assessment.
- For each AE/SAE, the investigator **must** document in the medical notes that he/she has reviewed the AE/SAE and has provided an assessment of causality.

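### Does leaving licensed vaccines given shortly before consent off the CRF undermine the descriptive safety percentages?

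*Protocol*

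**What the plan says.** Protocol 6.5.2 permits influenza vaccine and other licensed nonpneumococcal vaccines; quadrivalent meningococcal conjugate vaccine must wait until after the Visit 2 blood sample. Where feasible, it recommends that licensed vaccines be given "at least 14 days (for nonlive vaccines) or at least 28 days (for live vaccines) before or after 20vPnC administration". This is advice, not a requirement.

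Protocol 6.5.3 sets the recording window: "any nonstudy vaccinations received from the time of signing of the ICD to Visit 2 will be collected and recorded in the CRF". Protocol 8.10.1 lists "Obtain a personally signed and dated ICD" among the Visit 1 steps before vaccination. Before the dose, the window therefore normally covers only the part of Day 1 after consent.

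The earlier vaccine history on the CRF is pneumococcal. It is 13vPnC for Cohorts 1 and 2. The Schedule of Activities adds: "For Cohorts 3 and 4, information on prior vaccination with 7vPnC or 13vPnC will be recorded, if available".

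SAP 3.4.3 takes prior vaccines as the protocol collects them, and SAP 6.5.4 summarizes what was collected.

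**The concern.** The spacing advice covers the time before and after 20vPnC, but the CRF can show whether it was followed only from consent onward. A child given a live vaccine ten days before Day 1 is eligible, may be dosed, and leaves no trace of that vaccine in the analysis data. A recent licensed vaccine is neither an exclusion nor a reason to delay. The nearest rules concern other things: "Participation in other studies involving investigational drug(s), investigational vaccines, or investigational devices within 28 days prior to study entry" is an exclusion about trials, and fever "or other acute illness within 48 hours before investigational product administration" is a delay criterion about illness.

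The study has a single arm, so no control group shares the background reactogenicity. If an earlier vaccine causes fever in Days 1 to 7, or an AE in the first month, the event counts in the 20vPnC percentage. A reader could not see how many children were in that position. If results were split by recorded vaccines only, those children would sit in the group without another vaccine.

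**Working it through.** **1. Is the gap closed elsewhere?** No.
- The Schedule of Activities row for nonstudy vaccinations refers to Protocol 6.5.3 and does not widen the window.
- Protocol 8.10.2 asks at Visit 2 only for vaccines since Visit 1.
- Protocol 5.2 and 5.5.1 contain no rule on recent licensed nonpneumococcal vaccines.
- Some SAP text after the main safety analyses is redacted, but an analysis there could not use data the protocol does not collect.

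**2. Does a planned result need the missing data?** Protocol Section 3 and SAP 2.1 define the safety estimands as percentages of participants who receive 20vPnC and report an event in the window. They do not attribute events to 20vPnC alone. Protocol 4.1 allows routine vaccines on the same day when separation is not feasible. The denominator and numerator are complete without pre-consent vaccine dates.

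**3. The plan's own safety figure.** Protocol Table 5 gives the chance of at least one AE among 200 children, 1 − (1 − p)^200:

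| True rate p | Table 5 | Recomputed |
|---|---|---|
| 0.1% | 18% | 18.1% |
| 0.5% | 63% | 63.3% |
| 1% | 87% | 86.6% |
| 2% | 98% | 98.2% |

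The table reproduces, and the missing item does not enter it.

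**4. How far could the pooled percentage move?** Neither input below is in the documents; both are assumptions. Let q be the share of a cohort with an unrecorded recent vaccine and d the excess fever in points. The shift is q × d.

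| q (children of 200) | d = 5 | d = 10 | d = 15 |
|---|---|---|---|
| 5% (10) | 0.25 | 0.5 | 0.75 |
| 10% (20) | 0.5 | 1.0 | 1.5 |
| 20% (40) | 1.0 | 2.0 | 3.0 |

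The excess pushes the observed rate up, so the fair comparison is the lower arm of the Clopper-Pearson 95% interval:
- 20/200 (10%): 6.2 to 15.0, lower arm 3.8. All 9 shifts are smaller.
- 10/200 (5%): 2.4 to 9.0, lower arm 2.6. Eight of 9 are smaller; 3.0 is not.

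A harsher assumption can exceed the interval. With q = 30% and d = 20 points the shift is 6.0, against a lower arm of 5.3 at an observed 20% (40/200, interval 14.7 to 26.2).

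**5. The misclassified split.** Assume 30% of a cohort is vaccinated on the same day, leaving 140 children with no recorded vaccine. The 10, 20 or 40 unrecorded children would be 7.1%, 14.3% or 28.6% of that group, and the shift runs from 0.071 × 5 = 0.4 to 0.286 × 15 = 4.3 points. At 14/140 (10%) the lower arm is 4.4, so 4.3 is just inside. At 7/140 (5%, interval 2.0 to 10.0) it is 3.0, so 4.3 is outside. This harm needs a split that no visible section plans.

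**The case for a change.** The best case for a change is that a single-arm study can show background reactogenicity only by describing co-exposure, and that the sponsor's own spacing advice shows separation was thought worthwhile. The cost is one look-back item, at sites that already check 13vPnC records. Investigators are told to consider "Alternative causes, such as underlying disease(s), concomitant therapy, and other risk factors", but that applies to AEs and SAEs, not to prompted diary events, and "The daily e-diary data will not be captured in the CRF".

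Part of this stands. Before consent, adherence to the spacing advice cannot be checked from CRF data, and the assumed shifts cannot be replaced by observed ones.

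The rest is weaker:
- Diary data go to the sponsor electronically for analysis, so being outside the CRF does not stop them being set beside recorded vaccines.
- Giving every unrecorded child the same excess fever is severe. As a yardstick only, the protocol prompts for reactions for 7 days after a dose, and much of a 14- or 28-day look-back lies outside a period of that length.
- A table split by any vaccine before or on Day 1 would merge earlier with same-day recipients and would not isolate the earlier ones. If the vaccinated group were 20 children, an observed 10% (2/20) would have an interval of 1.2 to 31.7.
- SAP 6.5.4 is not left empty on prior vaccines, because pneumococcal history is collected.

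**Conclusion.** No change is needed. The gap is one of CRF scope: nonpneumococcal vaccines given before consent are allowed and not recorded. The planned analyses still deliver the stated estimands, because these are pooled descriptions in a population where other vaccines are allowed, and exposure from consent to Visit 2 is captured by name, location and date. Under the main assumptions (5% to 20% exposed, 5 to 15 points of excess) the pooled shift is 0.25 to 3.0 points, mostly within sampling error at 200 per cohort. More extreme assumptions would exceed it, and nothing in the documents shows which apply.

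A sponsor who wanted to check the spacing advice before the dose could extend the recording window and list earlier vaccines separately from same-day ones. That would be optional. Sample size, alpha, the primary tables and the conclusions drawn from them would stay the same, and a non-randomized breakdown would still not attribute events to either vaccine.
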